Due to the pilot nature of this study, formal power analysis and sample size estimation is not essential. Nevertheless, we attempted to estimate the potential treatment efficacy in this study. We considered the outcome measure for efficacy evaluation is the time to first stenosis event during the study period. From our recent clinical data, it was estimated that approximately 36% of dialysis patients experienced stenosis event at one-year follow-up. We would expect that patients in the new drug arm would have 10% stenosis event rate at one-year follow-up, compared to the 36% stenosis event rate in the placebo group. With these considerations, the analysis of stenosis-free survival will require at least 21 events, which is the number of events needed for one-sided log-rank test at 5% significance level to have 80% power to show statistically significant difference when the true hazard ratio is 0.236. This estimation will result in that approximately seventy patients will be needed and evenly randomized into each study arm (35 patients in Ticagrelor and 35 in placebo). This is an open-label study. Upon completion of all the required screening assessments, eligible patients will be randomly assigned to the study drug or placebo at 1:1 ratio with a block size of 20 in accordance with the randomization schedule. The randomization schedule will be provided by the Department of Public Health, School of Medicine. Patients will be identified by unique subject identifier that will remain consistent for the duration of the study. The active study period is 6 months followed by 6 months of monitoring, and accrual rate is approximately 12 patients per month. To compensate for an estimated drop-out rate of 25%, we will recruit 88 patients to the study.

4. What is your plan for primary variable analysis?

We have recruited/consented a total of 54 subjects into this study. We have enrolled a total of 43 patients into the study, 23 in the Ticagrelor treatment arm and 20 in the placebo arm. We will evaluate the safety of Ticagrelor in hemodialysis patients with AVF vascular access by tabulating adverse events and severe adverse events for the two study arms, and the difference between the two arms will be tested by chi-square test.

5. What is your plan for secondary variable analysis?

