For the secondary outcome, i.e., time to the first stenosis event, we will compare stenosis-free survival of Ticagrelor versus placebo using the Kaplan-Meier method. Survival probabilities and corresponding 95% confidence interval (CI) will be calculated at landmark time points for each arm, and survival difference between the two arms will be evaluated using a one-sided log-rank test stratified by the history of stenosis. Further, a stratified Cox proportional-hazards model will be used to derive the hazard ratio and 95% CI between the two regimens.

6. Have you been working with a statistician in designing this protocol?

Yes

IRB-HSR# 17224: Randomized, Placebo-controlled, Single Blind, Trial to Determine the Safety and Efficacy of Ticagrelor for Maintaining Patency of Arterio-Venous Fistulae Created for Hemodialysis

IF YES, what is their name?

[name]

Biomedical Research

1. What will be done in this protocol?

Subjects will be in this study for 1 year. Up to eighty eight patients with ESRD on chronic HD and a functioning AVF will be enrolled. For statistical purposes we will need to have seventy people complete the study. Consent form will be obtained. History and dialysis parameters will be taken at the screening visit. At the screening visit we will also be collecting a serum sample to perform a pregnancy test on female subjects of child bearing potential. This will be collected in a 3.5ml gold top serum separating tube. Study participants will be on the study medication (Ticagrelor) or placebo for six months (Visit 1 to Visit 12). Subjects will take the study medication twice a day. They will take it once in the morning and once in the evening. We will also instruct them to try and take it around the same times each day if possible. We will be collecting study medication to check for compliance at Visits 3, 6, 9, and 12. There will be a follow up for these subjects for six months (Visit 13 to Visit 18). Subjects will have a physical performed at screening, visit 12 (this is the last visit when subjects are on medicine), and at visit 18 which is the end of the study. We will be looking at hemoglobin levels that are collected as standard of care two times a month. We will be collecting the bleeding time weekly as well. This will be done at all visits (screening to Visit 18) which we define as the time it takes for a subjects' access to stop bleeding.

The following data will be documented on each subject at screening:

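### The sample-size section claims 80% power with about 70 patients and 21 events, but the analysis plan reports 43 enrolled; the plan does not say whether 43 is final or restate the power

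*Combined protocol and SAP*

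**What the plan says.** Statistical Considerations item 3 opens with a disclaimer: "Due to the pilot nature of this study, formal power analysis and sample size estimation is not essential". It then gives a calculation all the same. The endpoint is time to first stenosis ("We considered the outcome measure for efficacy evaluation is the time to first stenosis event during the study period"), and the assumption is that the "new drug arm would have 10% stenosis event rate at one-year follow-up, compared to the 36% stenosis event rate in the placebo group". From this it concludes that "the analysis of stenosis-free survival will require at least 21 events", the number said to be needed for a "one-sided log-rank test at 5% significance level to have 80% power" "when the true hazard ratio is 0.236". That leads to about 70 patients, 35 per arm, with 88 recruited to cover 25% dropout.

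Item 4, headed as the plan for primary variable analysis, reports 54 consented and then: "We have enrolled a total of 43 patients into the study, 23 in the Ticagrelor treatment arm and 20 in the placebo arm". Item 5 keeps the one-sided log-rank test, stratified by history of stenosis, for the secondary outcome.

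The targets of 70 and 88 also remain under Human Participants. Biomedical Research item 1 still allows up to 88 to be enrolled and adds: "For statistical purposes we will need to have seventy people complete the study". The documents nowhere say that enrolment closed at 43, that it continues, or what power 43 patients would give.

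**The concern.** Two adjacent items of one section describe trials of different sizes. A reader of item 3 takes away 80% power for the efficacy comparison. A reader of item 4 sees an enrolment about 60% of the planned 70 (43/70 = 0.61). If the analysis is run on 43, a non-significant log-rank result could be read as evidence against a large effect, on the strength of a power that the trial did not have. The event requirement in item 3 would also be out of reach, although that is only partly due to the smaller enrolment, as the working shows.

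**Working it through.** **Inputs.** From item 3: one-year event rates 10% (ticagrelor) and 36% (placebo), HR 0.236, one-sided 5%, 80% power, 35 per arm, dropout 25%, 12 months on study. From item 4: 23 and 20 patients.

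**The plan's own figures.**

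- Hazard ratio: ln 0.90 / ln 0.64 = 0.236. Confirmed.
- Events, with (1.645 + 0.842)² = 6.18:
  - Freedman: 6.18 × (1.236/0.764)² = 16.2, so 17.
  - Schoenfeld: 4 × 6.18 / (ln 0.236)² = 11.9, so 12.
  - Neither gives 21. Two other settings do: Freedman at two-sided 5% and 80% power (20.5), and Schoenfeld at two-sided 5% and 90% power (20.2). The documents do not say where 21 came from.
- Patients: the mean event rate is (0.10 + 0.36)/2 = 0.23, and 16.18/0.23 = 70.4. So 70 patients follows from one-sided Freedman.
- Events at 35 per arm: 35 × 0.10 + 35 × 0.36 = 16.1. To expect 21 would take 21/0.23, about 91 patients. By binomial calculation, the chance of 21 or more events at 35 per arm is about 10%.
- Power at 35 per arm with 16.1 events: 80% (Freedman) or 89% (Schoenfeld).

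The 70 patients and the 80% power therefore agree with each other. The 21 events agrees with neither.

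**Expected events at 23 and 20.**

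- No dropout: 23 × 0.10 + 20 × 0.36 = 2.3 + 7.2 = 9.5.
- 25% dropout spread exponentially over the year: observed event probabilities fall to 0.087 and 0.316, giving 23 × 0.087 + 20 × 0.316 = 8.3.
- 25% dropout, with dropouts contributing no events: 0.75 × 9.5 = 7.1.

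**Power at 23 and 20, one-sided 5%, HR 0.236**, for d events:

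- Freedman, with φ = 23/20 = 1.15: Φ(√(dφ) × (1 − HR)/(1 + φHR) − 1.645). At d = 9.5: Φ(3.305 × 0.764/1.271 − 1.645) = Φ(0.341) = 63%.
- Schoenfeld, with p = 23/43: Φ(√(d·p(1 − p)) × |ln HR| − 1.645). At d = 9.5: Φ(1.537 × 1.444 − 1.645) = Φ(0.575) = 72%.

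| Assumption | Events | Freedman | Schoenfeld |
|---|---|---|---|
| 35 and 35, no dropout | 16.1 | 80% | 89% |
| 23 and 20, no dropout | 9.5 | 63% | 72% |
| 23 and 20, dropout over the year | 8.3 | 59% | 67% |
| 23 and 20, dropouts give no events | 7.1 | 53% | 61% |

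A simulated unstratified log-rank test (20,000 runs, exponential times, censoring at 12 months) gave 68% at 23 and 20 without dropout, and 63% with dropout spread over the year. Stratification by history of stenosis was not modelled, because the documents give no stratum sizes or rates.

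**The case against.** The strongest reply is that 43 may be only a count to date. Item 4 reads like a status update entered in a live form, and Biomedical Research item 1 still allows up to 88. This stands. A reader might infer that the trial closed at 43 and is therefore underpowered, but no text says so. If enrolment continues to 70, there is no loss of power, only a misplaced status line.

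A second reply is that the trial is a pilot. Item 3 says a formal power analysis is not essential, feasibility and safety are the primary objective, and stenosis-free survival is secondary. This also stands and limits the importance of the point. It does not justify leaving an 80% figure beside an enrolment that would not give it. Item 5 still plans a one-sided test, and the stated hypothesis is that ticagrelor preserves patency better than placebo.

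Third, a reader might set 9.5 events against 21 and blame the whole gap on enrolment. The documents do not support that, because the full 35 per arm would yield only 16.1. The like-for-like fall is from 16.1 to 9.5.

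**Conclusion.** The point holds conditionally. Items 3 and 4 are unreconciled as they stand, whichever number is final. If 43 is the analysis set, the plan's own assumptions give about 7 to 10 events and about 53% to 72% one-sided power, depending on formula and dropout. Every variant tried is below the stated 80%. These figures assume exponential event times, 12 months of follow-up and the plan's 10% and 36% rates.

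Independently of enrolment, the 21-event figure is wrong for the stated one-sided 5% test at 80% power, while 70 patients is consistent with that power. The consequence is confined to the secondary efficacy comparison. No power is stated for the primary feasibility and safety objective, so this point does not affect it.

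**What to change.** State in item 3 whether enrolment ended at 43.

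- **If it did:** replace the 70 patients, 21 events and 80% power with 43 patients (23 and 20), about 7 to 10 expected events and about 53% to 72% power at HR 0.236, naming the formula and dropout assumption. Label the efficacy test exploratory, in keeping with the pilot status. Bring the 70 and 88 under Human Participants and Biomedical Research into line.
- **If enrolment continues:** say so, move the 54 and 43 out of the analysis plan as an interim status, and correct the 21 events to match the stated one-sided test (about 16 to 17 by Freedman).

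The cost is a few sentences and, in the first case, a less favourable stated power. No extra patients are needed.

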IRB-HSR# 17224: Randomized, Placebo-controlled, Single Blind, Trial to Determine the Safety and Efficacy of Ticagrelor for Maintaining Patency of Arterio-Venous Fistulae Created for Hemodialysis

► IF YES, who will generate the randomization scheme?

UVa Statistician: [name]

2. What are the statistical considerations for the protocol?

Since Ticagrelor has not been used in hemodialysis patients for the purpose of preventing thrombosis in dialysis vascular accesses (Arterio-Venous Fistulae and Grafts), this study is designed as a pilot study in that patients are randomly assigned to receive Ticagrelor or placebo drug for a six-month treatment period plus an additional 6-month follow-up period. The primary objective is to evaluate the feasibility and safety of Ticagrelor in hemodialysis patients with AVF vascular access. The secondary objective is to evaluate the treatment efficacy in that whether Ticagrelor will preserve patency of hemodialysis vascular access better than Placebo. The study will follow intent-to-treat principle and all randomized patients will be included in the analyses for the primary and secondary objectives.

3. Provide a justification for the sample size used in this protocol.

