1-Age/gender/race/body weight/cause of ESRD

2-Vintage of HD

3-Time since access was placed

4-Type and place of access and blood flow rate of access

5-History of prior access problems

6-Comorbid conditions (Example: Hypertension, coronary artery disease, Diabetes Mellitus, Bleeding problems, peripheral vascular disease).

7-Current medications (Example: Coumadin, Erythropoiesis stimulating agents, heparin, other antiplatelets, digoxin, statins)

This data will be obtained from the dialysis computer system and will be verified with the subject.

8-Physical Exam

9-Vital signs (blood pressure, heart rate, and weight) will be obtained from the subject's dialysis record.

Adverse events and concomitant medications will be reviewed at each study visit. We will also note any access issues at each study visit.

Study Medication Stopping Rules for Prolonged Bleeding:

If post treatment bleeding time is prolonged more than 30 minutes we will stop the study drug and refer for fistulogram,

If bleeding still persists after fistulogram and intervention we will continue to hold the study drug and do work up for bleeding. We will continue to hold study drug for 5 days if signs of increased tendency for bleeding as recurrent Epistaxis > twice in one week, if any evidence of GI bleed, or if Hgb should drop > 1gm in one week. If the bleeding is believed to be drug related or it no resolution occurs the subject will be withdrawn from the study.

We will also hold study drug for 5 days if hemoglobin is consistently less than 8g/dL for 2 consecutive weeks, or hemoglobin dropping 1g/dL in one week.

IRB-HSR# 17224: Randomized, Placebo-controlled, Single Blind, Trial to Determine the Safety and Efficacy of Ticagrelor for Maintaining Patency of Arterio-Venous Fistulae Created for Hemodialysis

For a prolonged bleeding event standard practice will be applied, including: (prolonged bleeding is defined as bleeding more than 30 minutes)

- **Direct pressure.** Any bleeding that warrants an emergency department visit should be immediately controlled with the application of direct digital pressure to the puncture site for 5-10 minutes. Once the bleeding abates, the patient should be observed for rebleeding or early thrombosis for 1-2 hours.

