2.1 What are identified risks and plans to minimize risk

****Please Also Refer to the Investigator Brochure and the Package Insert for Brilinta/ Ticagrelor**

Adverse Events with Brilinta/Ticagrelor

Frequent complaints (seen in at least 3% of study participants) that have been reported during studies:

- Bleeding
- Dyspnea (Shortness of Breath)
- Cough
- Dizziness
- Nausea
- Atrial Fibrillation (Heart Rhythm Disorder)
- Hypertension (High Blood Pressure)
- Non-Cardiac Chest Pain

IRB-HSR# 17224: Randomized, Placebo-controlled, Single Blind, Trial to Determine the Safety and Efficacy of Ticagrelor for Maintaining Patency of Arterio-Venous Fistulae Created for Hemodialysis

- Diarrhea
- Back Pain
- Hypotension (Low Blood Pressure)
- Fatigue
- Chest Pain
- Headache

More Frequent complaints (seen in at least 6 to 7% of study participants) that have been reported during studies:

- Bradycardia (Slow Heart Rate)
- Elevated Serum Creatinine

There have also been cases of increased uric acid levels for subjects taking ticagrelor. A high uric acid level, or hyperuricemia, is an excess of uric acid in your blood. Uric acid is produced during the breakdown of purine, a substance found in many foods. Once produced, uric acid is carried in your blood and passes through your kidneys, where most of it leaves your body when you urinate. A high uric acid level may result in attacks of gout, but not everyone who has high uric acid gets gout, and not everyone with gout has high uric acid. Increased uric acid may also increase the chances of kidney stones. There is also an increased risk of severe bleeding for subjects taking ticagrelor. Due to the increase risk of severe bleeding there may be a risk of delay in any surgery that you may need while taking this study medication.

Expected Risks related to study participation.	Frequency
Reproductive Risks These are unknown at this time.	Minimized due to the requirements of this protocol.
Violation of subject’s privacy and confidentiality	Minimized due to the requirements of the privacy plan in this protocol

2.2 List by bullet format a summary of safety tests/procedures/observations to be performed that will minimize risks to participants:

- Study personnel will be checking on patients twice a month for six months while subjects are on study treatment and once a month while subjects are in the follow up visits.
- We will be monitoring the time it takes for the subject’s access to clot.
- AE monitoring at each visit

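### The primary safety analysis names no bleeding outcome, although bleeding is the harm the protocol guards against, and the documents conflict on which events would enter its table

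*Combined protocol and SAP*

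**What the plan says.** Statistical Considerations item 2 of the combined protocol and SAP states: "The primary objective is to evaluate the feasibility and safety of Ticagrelor in hemodialysis patients with AVF vascular access". Item 4, the primary variable analysis, gives the only safety analysis: "tabulating adverse events and severe adverse events for the two study arms, and the difference between the two arms will be tested by chi-square test". It does not state event categories, unit of analysis, significance level or sidedness. It reports enrolment of "43 patients into the study, 23 in the Ticagrelor treatment arm and 20 in the placebo arm"; item 3 had planned "35 patients in Ticagrelor and 35 in placebo".

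Bleeding is prominent elsewhere:

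- **Inclusion/Exclusion Criteria, items 2 and 3:** recent bleeding, bleeding disorders, gastrointestinal ulcers, intracranial hemorrhage and oral anticoagulant use are exclusions, the last expressly because of bleeding risk.
- **Biomedical Research item 1, stopping rules:** study drug is stopped or held for prolonged access bleeding, for "signs of increased tendency for bleeding as recurrent Epistaxis > twice in one week, if any evidence of GI bleed", and for hemoglobin falls.
- **Data and Safety Monitoring Plan 2.1:** "There is also an increased risk of severe bleeding for subjects taking ticagrelor".
- **Biomedical Research item 1:** access bleeding time is collected from screening to Visit 18. No analysis uses it.

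**The concern.** When a drug has one recognised main harm, the primary safety analysis should look at that harm directly. Here it does not, and the effect depends on which recording rule is followed.

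If every adverse event counts, subjects who have some other event count as affected whether or not they bleed, and the arms move closer together. If only related and serious events count, bleeds that lead to a hold of study drug but are not serious never reach the table. Relatedness would also be judged by an investigator who knows the arm.

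Either way, a non-significant chi-square could be read as reassurance about bleeding that the test was poorly placed to give. A bleeding category chosen after the arms have been compared would be post hoc for the primary objective.

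**Working it through.** **Plan's own figure.** There is none to reproduce. Item 3 says "formal power analysis and sample size estimation is not essential", and its one power statement, "one-sided log-rank test at 5% significance level to have 80% power", concerns time to stenosis.

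**Which events enter the table?** All references are to the Data and Safety Monitoring Plan unless stated.

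- Broad: 1.1 defines adverse events whether or not related. Biomedical Research item 1 has them reviewed at each visit. The serious adverse event reporting text has all serious events documented, related or not.
- Narrow: 3.1 answers No to recording all adverse events and keeps only those both related and serious.
- Relatedness is graded by the principal investigator (3.4), and investigators are unblinded (Statistical Considerations item 1).
- Recording continues through the off-drug follow-up (3.6), so item 4 as written would mix on-drug and off-drug events.

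**Power, broad reading.** From the documents: 23 ticagrelor and 20 placebo subjects, chi-square test. Assumed: per-subject counting, two-sided 5%, no continuity correction, bleeding 10% v 40%, and a non-bleeding background equal in both arms and independent of bleeding.

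Any-event rate = 1 − (1 − background) × (1 − bleeding).

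For example, at 80% background:
- placebo: 1 − 0.20 × 0.90 = 0.82
- ticagrelor: 1 − 0.20 × 0.60 = 0.88

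Power is the sum of the binomial probabilities of all pairs of counts for which the Pearson statistic is significant.

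| Background | Any event, placebo v ticagrelor | Power |
|---|---|---|
| 0% (bleeding only) | 10% v 40% | 63% |
| 10% | 19% v 46% | 47% |
| 30% | 37% v 58% | 29% |
| 50% | 55% v 70% | 17% |
| 80% | 82% v 88% | 7% |
| 90% | 91% v 94% | 3% |

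**Power, narrow reading.** Suppose the filter keeps half the bleeds in each arm: 10% × 0.5 = 5% and 40% × 0.5 = 20%.

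- No background, 5% v 20%: power 25%.
- 10% background, 1 − 0.9 × 0.95 = 14.5% v 1 − 0.9 × 0.80 = 28%: power 17%.

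**Sensitivity.**

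- Bleeding 5% v 35%: bleeding-only power 71% (59% with Yates correction). Any-event power is 16%, 12% and 3% at 50%, 70% and 90% background.
- Planned 35 per arm, 10% v 40%: bleeding-only 85%; any event 25% at 50% background and 11% at 80%.

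**Precision of a bleeding comparison.** At 23 v 20, with 10% on placebo, ticagrelor must reach 48% for 80% power. If 10% and 40% were observed, the standard error is √(0.10 × 0.90/20 + 0.40 × 0.60/23) = 0.122. The approximate 95% interval is then 30 ± 24 percentage points, or 6 to 54.

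**The case against.** A reader might infer that the plan pools all adverse events and that a bleeding effect would therefore vanish in the background. The documents do not establish that. Item 4 speaks of tabulating events; it neither says totals nor rules out tables by event type. Section 3.1, if followed, removes most of the background, and with 0% to 10% background and no bleeds lost, power is 47% to 63%, not 7%. Dilution and loss of bleeds cannot both operate in full. No background rate appears anywhere, so the high-background rows are illustrations.

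The severe-event comparison is a further point for the plan: it is not modelled above, it may have a much lower background, and severe bleeding is the risk that section 2.1 names.

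It can also be said that this is a pilot, that power is a weak yardstick, and that a bleeding-only test is underpowered too. Finally, an endpoint built from every hold criterion would be noisy. A hemoglobin trigger need not involve a bleed, and prolonged access bleeding is also a referral sign for stenosis, the efficacy outcome.

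All of this stands and limits the size of the claim and the form of the remedy. It does not supply a prespecified bleeding comparison, and the milder case under section 3.1 holds only if few bleeds are filtered out.

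**Conclusion.** The point holds as an omission in the primary safety analysis: no bleeding outcome is prespecified, and the rules for which events are counted contradict each other. The gap is plain from the text. Its size is not.

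Under the assumed 10% v 40%, the planned test's power for the bleeding rise falls from 63% to anywhere between 47% and 3% as background goes from 10% to 90%. It is 17% to 25% if the filter keeps half the bleeds equally in both arms. With unblinded relatedness judgments, equal retention is itself uncertain. The conclusion does not extend to the severe-event comparison, whose background the documents do not give.

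Naming a bleeding outcome is a cheap improvement. It gives an interpretable estimate, not adequate power, at 43 patients.

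**What to change.** 1. Reconcile Data and Safety Monitoring Plan 3.1 with 1.1, the serious adverse event reporting text and the visit-level review in Biomedical Research item 1, so that one rule decides which events are recorded.
2. In Statistical Considerations item 4, before arms are compared, name the lead safety comparison: the proportion of subjects with at least one clinical bleeding event while on study drug, regardless of judged relatedness. Count the bleeds listed in the stopping rules, once those passages are reconciled, and any bleed that is serious under section 1.2. Report the arm difference with a 95% confidence interval.
3. Report hemoglobin-drop triggers and access bleeding beyond the protocol's threshold as separate components. The hemoglobin component also depends on reconciling how often hemoglobin is measured: twice a month in Biomedical Research item 1, weekly in section 2.2.
4. Keep total adverse and serious adverse events as supporting tables.

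The cost is SAP wording and one case-report-form line for the criterion met. The lead outcome needs no extra visits or tests. The downsides are that total events become supportive and the bleeding estimate will still be wide.

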- **Gelatin sponges.** Commonly seen in the emergency department as Gelfoam®, this adjunct may aid in the hemostasis of bleeding AV grafts. Although studies or case reports of this material being used in this setting are not found in the medical literature, our clinical practice has demonstrated success by including it in the management of this problem.

Life-Threatening Bleeding From Hemo Access

A vascular surgeon should be emergently consulted if hemorrhage cannot be quickly controlled. An adjunctive suture may be placed if there appears to be a small laceration of the graft rather than a puncture wound. This suture is used only after other measures to control bleeding described above have also failed.

Other life threatening bleeding: Subjects will be sent to the emergency department

2. Will you be using data/specimens in this study that were collected previously, with the use of a research consent form, from another research study?

No

3. List the procedures, in bullet form, that will be done for research as stipulated in this protocol.

- Physical Exams
- Administration of Investigational Drug
- HcG Blood Pregnancy Test
- Collection of Bleeding Time

Note: Laboratory data will be captured and recorded for research purposes from blood collected as part of the subject's clinical care-no additional blood is collected for the purpose of this study.

4. Will any of the procedures listed in item # 2 have the potential to identify an incidental finding?

Yes

► IF YES, check one of the following two options:

X The examination(s) utilize(s) the same techniques, equipment, etc., that would be used if the subject were to have the examination(s) performed for clinical care. There exists the potential for the discovery of clinically significant incidental findings.

- The PI takes full responsibility for the identification of incidental findings:
- The PI will inform the subjects verbally of all incidental findings that are of clinical significance or are of questionable significance.
- A follow-up letter describing the finding should be provided to the subject with instructions to either show the letter to their PC or if the subject has no PCP, the subject should be instructed to make an appointment at UVa or at the Free Clinic.

IRB-HSR# 17224: Randomized, Placebo-controlled, Single Blind, Trial to Determine the Safety and Efficacy of Ticagrelor for Maintaining Patency of Arterio-Venous Fistulae Created for Hemodialysis

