3.1 Will all adverse events, as defined in section 1.1, be collected/recorded?

No

► IF NO, what criteria will be used?

Only adverse events that are deemed related AND serious

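### Bleeding time is measured from screening to Visit 18 but never compared between arms, and the planned adverse-event table can miss a drug effect on it

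*Combined protocol and SAP*

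**What the plan says.** Statistical Considerations, item 2, makes feasibility and safety the primary objective. Item 4 gives the whole safety analysis: "tabulating adverse events and severe adverse events for the two study arms", with a chi-square test of the difference. Item 5 covers time to first stenosis only.

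The Data and Safety Monitoring Plan, section 2.1, lists bleeding among the drug's frequent complaints and adds: "There is also an increased risk of severe bleeding for subjects taking ticagrelor".

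Biomedical Research, item 1, defines bleeding time as how long the access takes to stop bleeding. On the schedule it says "We will be collecting the bleeding time weekly as well" and then "This will be done at all visits (screening to Visit 18". Item 3 includes "Collection of Bleeding Time" in its short list of procedures done for research.

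The stated uses are all at the level of the individual patient:
- Section 2.2 of the Data and Safety Monitoring Plan names the time to clotting of the access as a safety observation.
- The stopping rules in Biomedical Research, item 1, say: "If post treatment bleeding time is prolonged more than 30 minutes we will stop the study drug and refer for fistulogram". The same item defines prolonged bleeding as more than 30 minutes.
- The opening study summary and the section Hypothesis to be Tested make bleeding over 20 minutes after needle removal a trigger for a fistulogram.

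Section 3.1 of the Data and Safety Monitoring Plan says which adverse events are recorded: "Only adverse events that are deemed related AND serious".

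**The concern.** The trial asks whether ticagrelor is safe in dialysis patients, expects bleeding to be the main hazard, and times access bleeding repeatedly in both arms. The one planned between-arm safety comparison does not use those times. A long bleed reaches that comparison only if somebody records it as an adverse event. Under section 3.1 it must then be judged both related and serious. Section 3.4 gives the relatedness judgement to the principal investigator, and Statistical Considerations, item 1, says investigators and study personnel are un-blinded.

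At stake is the answer to the primary question. If ticagrelor lengthens access bleeding without producing events classed as serious and related, the safety table could look balanced while the trial's own measurements show a difference that nobody had planned to look at. A comparison first devised after un-blinded staff had seen the data would carry much less weight.

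**Working it through.** **Text check.** The table sets each mention of bleeding time beside its planned use.

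| Place | Use | Between arms? |
|---|---|---|
| Opening summary; Hypothesis to be Tested | Fistulogram referral above 20 min | No |
| Biomedical Research, item 1 (schedule) | Definition and collection | No |
| Biomedical Research, item 1 (stopping rules) | Stop drug and refer above 30 min | No |
| Biomedical Research, item 3 | Listed as a research procedure | No |
| Data and Safety Monitoring Plan 2.2 | Individual risk monitoring | No |
| Statistical Considerations, items 2 to 5 | Not mentioned | No |

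The aggregate review in section 5.3 of the monitoring plan includes endpoint data but specifies no such comparison.

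**Data available.** Item 4 reports 43 enrolled patients, 23 on ticagrelor and 20 on placebo. There are 12 treatment visits.
- Ceiling on treatment: 43 x 12 = 516 values, plus 43 at screening.
- If Visit 1 is measured before the first dose, which the protocol does not settle: 43 x 11 = 473.
- Both counts assume that every patient attends every visit. Weekly collection, if done, would give more.

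The plan states no figure on this point, so there is none to reproduce.

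**Precision of a difference in means.** One mean per patient; the documents give no SD, so results are in SD units.
- Standard-error factor: sqrt(1/23 + 1/20) = 0.3057.
- Unadjusted 95% half-width: t(41) x 0.3057 = 2.020 x 0.3057 = 0.617 SD.
- Adjusted for the screening value: 2.021 x 0.3057 x sqrt(1 - r²), where r, the correlation with screening, is an assumption.

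| Assumed r | Half-width (SD) |
|---|---|
| 0.3 | 0.589 |
| 0.5 | 0.535 |
| 0.7 | 0.441 |

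**Precision of a proportion.**
- 0/23 v 0/20: risk difference 0, Newcombe 95% CI -16.1 to +14.3 percentage points.
- Exact (Clopper-Pearson) two-sided 95% upper limit for 0/23: 1 - 0.025^(1/23) = 14.8%.
- Against 0/20, uncorrected Pearson chi-square: 4/23 gives p = 0.0502; 5/23 (22%) gives p = 0.0265.
- Fisher's exact test for 5/23 v 0/20 gives p = 0.051. The smaller expected count is 5 x 20/43 = 2.3, so the uncorrected test should not be leaned on.

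**The case against.** The strongest reply has four parts.

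**The adverse-event table already covers it.** Section 1.1 of the monitoring plan defines an adverse event broadly, bleeding is a listed drug reaction, and a bleed over 30 minutes triggers a drug stop and a fistulogram. Such a bleed can meet the definition. Section 3.7, the text on serious adverse event reporting and section 5.3 also point to wider recording than section 3.1. This stands in part: a reader might infer that long bleeds cannot appear in the table, and the documents do not support that. They do leave section 3.1 in force, and even complete event counts would not compare the minutes measured.

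**Bleeding time is also a sign of stenosis.** The 20-minute referral rule says so. If ticagrelor impairs haemostasis, bleeding lengthens; if it prevents stenosis, as hypothesised, bleeding may shorten. A difference in means can net the two. This stands, so such a difference cannot be read as a clean measure of harm, and a null mean could hide a real bleeding effect.

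**The values will be incomplete and are not blinded.** Human Participants, item 2, expects 25% screen failure, dropout and withdrawal, and the stopping rules withdraw patients whose bleeding is thought drug related. Values may be missing in those most affected. The people doing the timing know the arm. Both points stand: the minutes cannot be assumed available for every patient, and they are less exposed to judgement than a relatedness call, not free of it.

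**This is a pilot, and bleeding time serves its stated purpose.** A reader might infer that it is collected to no end or that the plan contradicts itself. Neither follows; it drives individual safety decisions. The pilot label is a reason to estimate and not to test. It is not a reason to leave the comparison unspecified.

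**Conclusion.** The gap is real and modest. No section compares bleeding time between arms, although safety is a primary objective, bleeding is a named drug risk, and the measurement is made for research throughout. As written, the adverse-event table can miss a drug effect on access bleeding. How much it would miss cannot be given in minutes or patients, because the documents contain no SD and no rate of long bleeds.

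The added analysis would be informative only within limits. The half-width is about 0.62 SD unadjusted, and 0.44 to 0.59 SD if the correlation with screening lies between the assumed 0.7 and 0.3. These figures assume that all 43 patients contribute. With no bleed over a cut-off in either arm, the data would still be compatible with up to about 15% of ticagrelor patients having one. The figure of 5 in 23 needed against none on placebo holds for the uncorrected chi-square only.

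This is an inexpensive improvement that should be made, as a supportive analysis and not as a replacement for the adverse-event table.

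**What to change.** Add to Statistical Considerations, item 4, before any bleeding data are summarised by arm, a supportive safety analysis limited to estimation:

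1. A by-arm table of patients with at least one on-treatment bleed over 30 minutes (the protocol's definition of prolonged bleeding) and, separately, over 20 minutes (labelled as the fistulogram-referral cut-off). Count bleeds whether or not they were recorded as adverse events, and give the risk difference with 95% CI.
2. The difference in mean on-treatment bleeding time by randomized arm, one mean per patient, adjusted for the screening value, with 95% CI. Use all available values as randomized, in line with the intent-to-treat statement in item 2, and report the number of patients and values contributing per arm. Add a sensitivity analysis using only values before the first drug stop or access intervention.
3. A statement that non-significance is not evidence of safety, and that a mean difference may combine impaired haemostasis with any effect on stenosis.

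The cost is an analysis-plan amendment and a small addition to the safety tables. No new procedure is needed, because the measurements are already required. The drawbacks are wide intervals at 23 v 20, un-blinded timing, values missing after withdrawal, and a mean that can be pulled toward no difference by drug stops or interventions that follow a long bleed.
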